### *Primary Outcome*

Total dose of remifentanil in mg.kg-1.h-1 will be compared using Wilcoxon Mann-Whitney test (assuming data will not necessarily follow a normal distribution).

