### **Inclusion criteria**

- Fully consented, ASA 1-3 patients from 18yo to 65yo
- Undergoing laparoscopic surgery associated with sub umbilical mini-laparotomy. Eligible surgeries will be hysterectomy (excluding vaginal approach) and left hemicolectomy, of duration time expected under 180 minutes, under général anesthesia
- No allergy to one of the medications used in this study

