### **Randomization and blinding**

Electronic randomization will be performed by a statistician using a computer-generated randomized sequence with a variable block size unknown to the investigators, and then implemented in a RedCAP™ application. It will be sealed in an opaque envelope and handed to the dedicated research staff not involved in patient care and responsible to prepare the blinded syringe. The envelope will be opened at the patient's entry into the operating ward, after confirming that the surgery will be performed. Once the group is assigned to the patient, the research staff will prepare a syringe containing the randomized solution, either esmolol or saline. Each 10ml ampoule contains 100mg of esmolol. Syringe preparation will depend on the patient's adjusted body weight (ABW) and the expected duration of surgery (DOS) in hour as indicated on the surgical booking request. The number of ampoules required (NA) will be calculated according to the following formula (rounded up to nearest whole number):

$$NA = \frac{ABW \times (0.5 + (1.2 \times DOS))}{100}$$

If a syringe recharge is needed during the surgery, a new blinded syringe containing the same substance as the previous one, will be prepared by the dedicated research staff and brought into the operating room.

The patient, the anesthesiologist, the surgeon, the PACU staff and the research team acting as outcome assessors, will all be blinded to the randomization.

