***Anesthesia maintenance during surgery:***

Nociception management: The remifentanil target controlled infusion will be set at 3 ng.ml prior to the surgical incision, and will be modified according to the NOL index, as described in Figure 1. If the NOL index is > 25 for more than 1 min, we will increase remifentanil TCI by 0.5 ng.ml. This rate will be decreased by steps of 0.25 ng.ml if the NOL index is < 10 for more than 3 min. The minimal remifentanil TCI concentration allowed in the protocol will be 1 ng ml, to ensure a minimal antinociception drug administration in case of inaccuracy of NOL

Index in either group. Furthermore, in the event of a TAM > 120% of its basal level, and despite a NOL Index between 10 and 25, remifentanil will be increased.

Only the **intervention** and **anesthesia maintenance** sections above differ from the usual management of patients under general anesthesia.

In both groups, IV hydromorphone 0.006 mg.kg and ondansetron 4 mg will be administered once pneumoperitoneum is deflated and skin suture is started. Local anesthetic infiltration of the wounds will be performed by the surgical team using a maximum of 30 ml de bupivacaine 0.5%. Remifentanil infusion will be stopped and removed at the start of wound dressing.

Hemodynamic management: Baseline mean arterial blood pressure (MAP) will be defined as the average of three consecutive values taken 1 min apart and determined before the induction of general anesthesia. Intravenous (IV) infusion of norepinephrine will be adjusted to maintain +/- 20% of the baseline values of the pre-anesthesia MAP. Balanced crystalloids will be administered to patients at a rate of 3 ml.kg.h (ABW) throughout the surgery. Intravenous fluid boluses will be administered at the discretion of the anesthesiologist in charge. Perioperative blood management will be done according to guidelines.

Depth of anesthesia management: The maintenance of anesthesia will rely on sevoflurane to reach [0.7–1.2] minimal alveolar concentration (MAC; MAC adjusted to the participant's age) and a BIS index of [40-60]. Sevoflurane will be discontinued when the wound dressing is completed, and participants will be extubated in the operating room and transferred to the post-anesthesia care unit (PACU).

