## **E. STATISTICAL PLAN**

### **Sample Size Determination and Power**

Based on a recent unpublished trial (MERK study) recently held at our center focusing on colorectal surgeries, we assumed a mean intraoperative remifentanil consumption of 5.59 mcg.kg-1.h-1 and 7.98, respectively in the intervention and control group, with a combined standard deviation of  $\pm 3.24$ . This data is aligned with recently published international data (Sabourdin et al., 2022). With an alpha risk of 5%, a power of 80.0%, a two-tailed test, and an estimated dropout ratio of 10.0%, it was calculated that 32 patients would be required in each group, to detect a 30% reduction in intraoperative remifentanil administration.

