### **Statistical Methods**

Descriptive statistics will be presented by groups using mean and standard deviation, or median and interquartile range if the distribution is skewed or not normal for continuous parameters (according to the skewness of the distribution of each parameter). Frequency (%) will be used for categorical parameters. According to the nature of the analyzed endpoints, confidence intervals (CIs) between proportions or between means/medians differences will be presented. Missing data will be replaced by the maximum value observed (worst-case scenario). Risk differences or mean differences with 95% confidence intervals will be reported for all outcomes. The alpha value will be set at 0.05 to establish statistical significance. All data will be analyzed by the intention to treat principle. All statistical analysis will be performed using SAS, SPSS software or python programming language via VS Code or Jupyter notebook software.

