### **Study Timetable**

Depending on validation by the ethical authorities, inclusions should begin in February or March 2024. Given the study population, we estimate that we will be able to include a target number of subjects by September or October 2024. Data consolidation will be completed one month following the last enrollment.

Analysis and publication should follow shortly thereafter.

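### Should the primary Wilcoxon test have been stratified by procedure (hysterectomy or left hemicolectomy)?

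*Protocol*

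**What the plan says.** Protocol, Primary Outcome: the remifentanil dose in the two arms "will be compared using Wilcoxon Mann-Whitney test (assuming data will not necessarily follow a normal distribution". No stratum or covariate is named.

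Protocol, Inclusion criteria: "Eligible surgeries will be hysterectomy (excluding vaginal approach) and left hemicolectomy". Both are laparoscopic with a small incision below the umbilicus.

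Protocol, Randomization and blinding: allocation follows a "computer-generated randomized sequence with a variable block size unknown to the investigators". Procedure is not mentioned as a stratum.

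Protocol, Sample Size Determination and Power: the planning means and SD come from an unpublished trial at the same centre "focusing on colorectal surgeries".

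Protocol, Anesthesia maintenance during surgery: for every patient the remifentanil target starts at the same value, "will be modified according to the NOL index, as described in Figure 1", and has the same lower limit.

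Protocol, Statistical Methods: "Risk differences or mean differences with 95% confidence intervals will be reported for all outcomes". Adjustment is not mentioned.

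The protocol states neither an expected difference in remifentanil use between the two operations nor their expected proportions.

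**The concern.** Using a prognostic baseline factor in the analysis is usually sound advice, and procedure is known for every patient before randomisation. If hysterectomy and left hemicolectomy need different remifentanil rates, pooling them widens the spread that the plain rank test has to overcome. The planning SD mentions no hysterectomy patients, so that extra spread might not have been budgeted for. Without stratified allocation, chance can also put more of one operation in one arm. In a trial of 64 patients there is little power to spare.

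At stake would be power and precision only. The concern does not touch bias or the false-positive rate.

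**Working it through.** **1. The plan's own figure.** Inputs from Sample Size Determination and Power: means 5.59 and 7.98 mcg/kg/h, SD 3.24, two-sided 5%, power 80%, dropout 10%.

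- Difference: 7.98 − 5.59 = 2.39, which is 2.39/7.98 = 29.9%.
- Standardised effect: 2.39/3.24 = 0.738.
- n per arm = 2 × (1.960 + 0.842)² × (3.24/2.39)² = 28.85, rounded up to 29.
- Dropout: 29 × 1.1 = 31.9, so 32, the stated figure. (29/0.9 = 32.2 would give 33.)

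**2. Is the plain test valid when two procedures are pooled?** Yes. Randomisation makes the arms comparable under the null whatever the procedures do. Simulated rejection under the null is 4.9% to 5.0% (normal data, procedure gap g of 0, 2 and 3.24 mcg/kg/h, mixes 50:50 and 85:15). In a second simulation with normal and log-normal data and gaps of 0 and 1 SD it is 4.6% to 5.2%. The stratified alternatives fall in the same ranges.

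**3. Would using procedure add power?** Assumptions: 29 evaluable per arm, effect 2.39, 3.24 taken as the SD within a procedure, normal data, unstratified allocation, 200,000 simulated trials per setting. The gap g and the mix are not in the protocol, so ranges are shown. The alternative centres values within each procedure, ranks them jointly and takes the variance within procedure (aligned-rank test).

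| g (mcg/kg/h) | Plain, 50:50 | Aligned, 50:50 | Change at 50:50 / 70:30 / 85:15 (points) |
|---|---|---|---|
| 0 | 76.8% | 76.1% | −0.7 / −0.8 / −0.8 |
| 1 | 75.8% | 76.0% | +0.2 / +0.1 / −0.2 |
| 2 | 72.7% | 75.8% | +3.2 / +2.5 / +1.1 |
| 3.24 | 66.9% | 76.0% | +9.0 / +7.4 / +4.2 |

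(Changes come from unrounded power. The larger share in each mix is left hemicolectomy.)

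- Break-even, normal data: g of about 0.9 / 1.0 / 1.3 for the three mixes, that is 0.9/7.98 = 11% to 1.3/7.98 = 16% of the control mean.
- Break-even, log-normal data (assumed coefficient of variation 0.48, 30% proportional reduction): g of about 1.1 / 1.2 / 1.5. The change is −0.8 / −0.8 / −0.9 at g = 0 and +2.6 / +1.9 / +1.0 at g = 2.
- The van Elteren test is less favourable: −1.5 / −1.5 / −1.4 at g = 0, with break-even at about 1.3 / 1.35 / 1.7.

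**4. Second simulation.** With no gap, 29 per arm and a 50:50 mix, the plain test has 76.7% and the aligned test 75.9% (centred on means) or 75.7% (centred on medians). At 32 per arm the figures are 81.1%, 80.2% and 80.1%. Across all no-gap settings the cost is 0.7 to 1.05 points, the largest with median centring and log-normal data. At a gap of 1 SD the plain test has 66.8% and the aligned test 76.2%.

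**5. If 3.24 is the total SD instead.** The source trial covered colorectal operations in the plural, so 3.24 may already contain spread between operations. Holding the total SD at 3.24, plain against aligned power is 76.6% against 78.4% at a gap of half a within-procedure SD, and 76.1% against 84.5% at one. The possible gain is then similar or smaller in points, and the plain test stays close to its no-gap power of 76.7%.

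**6. Chance imbalance.** With 29 per arm and a 50:50 mix, the SD of the between-arm difference in procedure share is √(0.25 × 2/29) = 0.131. At a gap of 1 SD this moves the group difference by 0.131 × 3.24 = 0.43 mcg/kg/h. It is random error and is already in the standard error: 0.850 unadjusted against 0.857 adjusted at g = 0, and 0.890 against 0.859 at g = 2.

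**The case for a change.** The best argument for stratifying is that the trade is lopsided. The premium is about one point of power. The cover is 4 to 9 points at a gap of 3.24 and about 20 points at 1.5 SD in a 50:50 mix (75.6% against 55.7%). The aligned test stays near 76% throughout. The trial also has no slack, since the plain test with 29 normal observations per arm is already near 77%.

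The arithmetic stands, but it does not make the chosen test wrong.

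- The large gains need a gap for which the protocol gives no sign. A gap of 3.24 exceeds the treatment effect of 2.39 and is 3.24/7.98 = 41% of the control mean. Both operations share the surgical approach, the titration rule and the lower limit of the remifentanil target, which argues against a difference of that size.
- The shortfall from 80% is there at g = 0, so pooling does not cause it. The aligned test makes it slightly larger (76.8% to 76.1%).
- A change of primary test has its own costs. The method is less common, and centring on means or medians would have to be settled. Statistical Methods replaces missing values by the observed maximum, which would shift the procedure centres; the simulations used complete data and do not cover this. Study Timetable says "we estimate that we will be able to include a target number of subjects by September or October 2024", so a change could come late.

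A procedure-adjusted analysis is also something a separate statistical analysis plan, not available here, may contain. As a supportive analysis it would be harmless, but it would not alter the primary conclusion.

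**Conclusion.** The concern does not hold. The plain Wilcoxon test is stated clearly, suits an outcome that may be skewed, and keeps its 5% level whether or not the procedures differ. Nothing in the protocol on this point is wrong or contradictory.

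What remains is a matter of preference. Aligning by procedure costs 0.7 to 1.05 points of power if procedure does not matter, is neutral at a gap of about 0.9 to 1.5 mcg/kg/h, and gains about 1 to 3 points at 2. Since the protocol supplies neither the gap nor the mix, the expected gain has not been shown to be positive, and statisticians could reasonably choose either test.

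These sizes rest on 29 complete observations per arm, a true difference of 2.39, 3.24 as the within-procedure SD, and mixes from 50:50 to 85:15. Evidence of a procedure gap well above 2 mcg/kg/h would change the balance on efficiency, but would still not make the plain test invalid.

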### *Secondary Outcome*

Intraoperative and postoperative data collected in the groups will be compared using parametric (Student t-test) or nonparametric tests (Mann-Withney U test) depending on the type of variables and their distribution, and a chi-square test will be used for proportion. Data collected over time on categorical variables or on those which are not normally distributed will be analyzed with non-parametric tests.

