### **Secondary endpoints**

- The NOL Index variation before and after orotracheal intubation and first surgical incision. NOL index will be evaluated 3 minutes after stimulation to record the maximum value and calculate the area under the curve;
- The mean intraoperative BP and HR;
- The intraoperative doses and time weighted average of norepinephrine (mg); ephedrine (mg), glycopyrrolate (mg) and atropine (mg);
- Total time and time weighted average with NOL value above > 25;
- The total time and time weighted average of hypotension (< 20% of the baseline values of the pre-anesthesia mean arterial pressure (MAP) and/or bradycardia (HR < 60 beats/min, or HR < 50 beats/min for a profound bradycardia)) during surgery;
- The time to first analgesic requirement in PACU;
- The amount of morphine equivalent consumption for postoperative pain relief in the post anesthesia care unit (PACU) in both groups.
- The intensity of pain at rest and under stress, using a verbal rating scale (VRS), from arrival to discharge from PACU.

- The Silvermann Integrated Approach (SIA) Score (combining pain score and opioid consumption);
- Postoperative outcomes such as postoperative nausea and vomiting (PONV) and amount of antiemetics used in PACU;
- The time spent in PACU (in minutes);

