**O. FIGURE 1**

\* Minimum remifentanyl TCI Ce = **1ng.ml**

\*\* Baseline mean HR (mmHg) & HR (bpm) determined before induction

**In case of major hemodynamic instability, mainly due to refractory bradycardia, blinded syringe's infusion can be discontinued at the anesthesiologist's discretion.**

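### Mean intraoperative BP and HR are compared without baseline adjustment although pre-treatment values are recorded: valid, but precision is lost, potentially much for MAP and by an unknown amount for HR

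*Protocol*

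**What the plan says.** - **Endpoint.** Protocol, Secondary endpoints, lists "The mean intraoperative BP and HR".
- **Test.** Under Secondary Outcome in the Statistical Plan, intraoperative and postoperative data "will be compared using parametric (Student t-test) or nonparametric tests (Mann-Withney U test"), the choice depending on variable type and distribution. Neither this section nor the general Statistical Methods text names a covariate or a change from baseline.
- **Baseline MAP.** The hemodynamic management paragraph says it is "defined as the average of three consecutive values taken 1 min apart and determined before the induction of general anesthesia".
- **Link from baseline to outcome.** The same paragraph states: "Intravenous (IV) infusion of norepinephrine will be adjusted to maintain +/- 20% of the baseline values of the pre-anesthesia MAP".
- **Baseline HR.** It appears only in the Figure 1 footnote: "Baseline mean HR (mmHg) & HR (bpm) determined before induction". The mmHg unit suggests that the first item was meant to be MAP. The figure itself is not in the text at hand, and the readable text has no rule that holds HR to its baseline.
- **Timing of the study drug.** The Intervention paragraph starts the esmolol or saline bolus together with remifentanil, at induction.
- **Use of the result.** The Hypotheses section expects the remifentanil saving to come with no haemodynamic effect, and Statistical Methods promises differences with 95% CIs for all outcomes.

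**The concern.** Both baselines precede the study drug, so esmolol cannot have influenced them. They may be read after the allocation envelope is opened, but they are read before treatment, and care staff are blinded. They are therefore legitimate covariates. For MAP the protocol itself creates a correlation, because in both arms a patient's intraoperative pressure is pulled towards that patient's own starting value. Part of the between-patient spread in mean intraoperative MAP is then baseline spread, and a two-sample test counts it as noise.

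At stake is the width of the interval behind the no-haemodynamic-effect hypothesis. A non-significant difference with a wide interval is weak evidence of neutrality, and the protocol lists hypotension and bradycardia among esmolol's adverse reactions. The protocol also already measures hypotension against each patient's own pre-anesthesia MAP, so it uses baseline as the reference for one pressure endpoint and not for the other.

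**Working it through.** **1. Number of patients.** The protocol's only sample size is for remifentanil: means 5.59 and 7.98 (difference 2.39), SD 3.24, two-sided alpha 5%, power 80%, dropout 10%, 32 per group.

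n = 2 × (1.960 + 0.842)² × (3.24 / 2.39)² = 28.9, so 29 per arm. Then 29 × 1.1 = 31.9, which rounds up to the stated 32 (29 / 0.9 would give 33). The figure reproduces to within a patient and does not bear on this point, except that about 29 per arm should be evaluable.

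**2. Precision without adjustment, 29 per arm.** The standard error of a mean difference is SD × √(2/29) = 0.263 SD.
- 95% CI half-width: 2.003 × 0.263 = 0.53 SD (t quantile on 56 degrees of freedom).
- Difference detectable with 80% power: 2.802 × 0.263 = 0.74 SD.

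**3. Effect of adjustment.** With within-arm correlation r, the variance is multiplied by 1 − r², the CI width by √(1 − r²), and the equivalent sample by 1/(1 − r²). This ignores the one degree of freedom spent on the covariate, which matters little with 58 patients.

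| r | Variance left | CI width factor | Equivalent sample | Detectable difference (unadjusted SD) |
|---|---|---|---|---|
| 0.3 | 0.91 | 0.95 | 1.10 | 0.70 |
| 0.4 | 0.84 | 0.92 | 1.19 | 0.67 |
| 0.5 | 0.75 | 0.87 | 1.33 | 0.64 |
| 0.6 | 0.64 | 0.80 | 1.56 | 0.59 |
| 0.7 | 0.51 | 0.71 | 1.96 | 0.53 |
| 0.8 | 0.36 | 0.60 | 2.78 | 0.44 |
| 0.9 | 0.19 | 0.44 | 5.26 | 0.32 |

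**4. What r might be for MAP.** The protocol gives no SD and no correlation for BP, so everything here is assumed. Let baseline B have mean 93 mmHg and SD s, and let intraoperative MAP be B × F, with F independent of B, mean m and variance v. Then

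r = m·s / √(m²s² + 93²v + s²v).

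Example: F uniform on 0.8 to 1.2 has m = 1 and v = 0.4²/12 = 0.0133. With s = 8, r = 8 / √(64 + 115.3 + 0.9) = 0.60.

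| Assumed F | s = 8 | s = 10 | s = 12 | s = 15 |
|---|---|---|---|---|
| Uniform 0.8 to 1.2 | 0.60 | 0.68 | 0.74 | 0.81 |
| Mean 0.9, SD 0.10 | 0.61 | 0.69 | 0.76 | 0.82 |
| Uniform 0.8 to 1.0 | 0.80 | 0.86 | 0.89 | 0.93 |
| Mean 0.9, SD 0.05 | 0.84 | 0.89 | 0.92 | 0.94 |

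The extremes, 0.60 and 0.94, correspond to 35% and 89% of the variance removed. The rounded range of 0.6 to 0.9 gives 36% to 81%.

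**5. HR.** No readable rule ties HR to its baseline, so step 4 cannot be repeated. At an illustrative r of 0.3 to 0.6, adjustment removes 9% to 36% of the variance.

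**The case against.** The case for leaving the text alone has four parts.

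- **The test is valid.** Randomisation justifies an unadjusted comparison, and its standard error already allows for chance baseline imbalance. This stands: a reader might infer bias, but the only loss is efficiency.
- **Covariates are commonly left to the SAP, which is not at hand.** This stands in part. The protocol does not leave the method open, however. It names the tests for intraoperative data, and a later ANCOVA would depart from them.
- **The MAP correlations are built into the assumed model.** The model makes F independent of baseline and, in the uniform rows, assumes perfect adherence to the 20% band. If patients with high pre-induction readings fall proportionally more, r is lower. This stands, and it is why the gain is only a range.
- **Other endpoints also bear on haemodynamic effect.** Time in hypotension, time in bradycardia and vasopressor doses are listed too. Because norepinephrine is titrated in both arms, part of any pressure effect should appear in its dose rather than in mean MAP. Baseline adjustment cannot undo that damping. This stands and lowers the weight of the point.

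Two stronger readings are tempting. A reader might infer that most of the precision is thrown away. Removing more than half of the variance needs r above √0.5 = 0.707, and the protocol gives no r; the full-band rows above fall short of that at baseline SDs of 8 and 10. A reader might also carry the titration argument over to HR, but the readable text ties only MAP to its baseline.

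**Conclusion.** The point holds as a loss of efficiency in a secondary comparison. The protocol fixes an unadjusted test where a pre-treatment covariate is already recorded. The gain from using it is potentially large for MAP and of unknown size for HR, within the assumed ranges worked out above. For MAP an r of 0.6 would narrow the interval by 20% and an r of 0.8 by 40%, but neither value comes from the documents.

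Nothing here touches the remifentanil analysis or the 32 per group. The weight is modest, and the case for acting rests mainly on the change being free.

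**What to change.** In the Secondary Outcome section, state that mean intraoperative MAP and mean intraoperative HR are each compared by ANCOVA, with arm as factor and the patient's own pre-induction MAP or HR as covariate. Report an adjusted mean difference with 95% CI, and keep the unadjusted comparison as a sensitivity analysis. Name MAP as the pressure analysed, since the endpoint says only BP. State how baseline HR is obtained, since only the Figure 1 footnote mentions it, and correct the label there. Fix the covariates before any unblinded analysis.

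The cost is a few lines of wording, with no new patients, no new measurements and no change to clinical management.

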### **Secondary Objectives**

Secondary objectives cover a wide range of concepts, including the hemodynamic impact of esmolol, the pain profile, and the incidence of opioid-related side effects. More specifically, we aim to :

1. compare NOL Index variation before and after orotracheal intubation and first surgical incision. NOL index will be evaluated 3 minutes after stimulations to record the maximum value and calculate the area under the curve ;
2. compare the mean intraoperative BP and HR;
3. compare the intraoperative requirements and time weighted average of norepinephrine, ephedrine, glycopyrrolate and atropine;
4. compare the total time and time weighted average with NOL value above > 25.
5. To compare the total time and time weighted average of hypotension and/or bradycardia during surgery;
6. compare the time to first analgesic requirement in PACU;
7. compare postoperative morphine equivalent consumption in the post anesthesia care unit (PACU);
8. compare the intensity of pain at rest and under stress, using a verbal rating scale (VRS), from arrival to discharge from PACU;
9. To compare Silvermann Integrated Approach (SIA) Score (combining pain score and opioid consumption);
10. assess postoperative outcomes such as postoperative nausea and vomiting (PONV) and amount of antiemetics used in PACU;
11. compare the time spent in PACU.

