## **Hypotheses**

The main hypothesis of this study is to show that patients receiving an intraoperative esmolol infusion during a NOL-guided general anesthesia, will consume a lower amount of intraoperative remifentanyl (mcg.kg-1.h-1) with a reduction of 20 to 30% of intraoperative opioid consumption, without impacting hemodynamic parameters. Upon reproducible nociceptive stimulation such as orotracheal intubation and initial surgical incision, we expect a reduction of the deltaNOL with the administration of esmolol, while still capturing the event on the PMD-200. Finally, once the patient reaches the PACU, we expect a longer time to first opioid, a lower pain score on arrival, a lower opioid consumption, a reduced incidence of PONV, and a shorter PACU stay.

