Neuromuscular blockade management: The TOF ratio will be maintained at 0/4 with repeated boluses of 0.1 mg.kg rocuronium. The patient's neuromuscular blockade will be reversed by sugammadex 2 mg.kg to and 4 mg.kg (TBW) according to TOF response, to obtain a minimum ratio of 0.9.

Patient management in PACU: patients will be transferred to the PACU, and as soon as sufficient contact is obtained by the PACU nurses the pain level will be assessed. In the PACU, all the postoperative criteria of the study will be assessed until time of readiness for discharge. According to standard practice, the attendant nurse will administer IV hydromorphone in PACU.

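### Time to first PACU analgesic: the planned tests, mean difference and maximum-value fill do not suit an endpoint that some patients may never reach before discharge

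*Protocol*

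**What the plan says.** The endpoint is listed in the protocol under Secondary Objectives ("compare the time to first analgesic requirement in PACU") and again under Secondary endpoints. The Hypotheses section gives its direction, "we expect a longer time to first opioid", and in the same sentence expects "a reduced incidence of PONV, and a shorter PACU stay".

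The paragraph on patient management in PACU (section C) sets the end of observation: "all the postoperative criteria of the study will be assessed until time of readiness for discharge".

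Three rules in section E then apply:

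- **Test** (Secondary Outcome): intraoperative and postoperative data "will be compared using parametric (Student t-test) or nonparametric tests (Mann-Withney U test) depending on the type of variables" and their distribution, with chi-square for proportions.
- **Effect measure** (Statistical Methods): "Risk differences or mean differences with 95% confidence intervals will be reported for all outcomes".
- **Absent values** (Statistical Methods): "Missing data will be replaced by the maximum value observed (worst-case scenario").

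The protocol names no time-to-event method. It does not say what value a patient has who leaves PACU without an analgesic, or whether that patient counts as missing.

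**The concern.** A patient who is ready for discharge without having needed an analgesic is right-censored: the time is known only to exceed the stay. Such patients are plausible, because both groups receive hydromorphone at skin suture and wound infiltration with local anesthetic.

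Three things follow.

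1. Longer is better for this endpoint, so the largest observed value is the most favourable one. The worst-case label is wrong here, and a patient whose time was simply not recorded would be credited with the best result in the trial.
2. If event-free patients also receive the maximum, the mean difference with its confidence interval depends on one extreme observation.
3. Whether event-free patients are filled in or left out is open, and the two readings give very different results. The expected shorter stay with esmolol would make the observation window differ between arms, which matters under both.

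At stake is the interpretation of one hypothesised secondary endpoint. The primary analysis and the sample size are not affected.

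**Working it through.** **Stated figure.** The protocol gives no design figure for this endpoint. Its group size, set for the primary endpoint, reproduces: 2 × (1.960 + 0.842)² × 3.24² / (7.98 − 5.59)² = 28.9, so 29 per group; 29 × 1.10 = 31.9, so 32. The check uses 32 per arm, without dropout.

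**Assumed inputs.** The protocol gives no median time to analgesic, PACU stay or event-free share. Assumed: exponential times, control median 30 min, hazard ratio 0.5, stay uniform from 60 to 120 min and independent of analgesic need.

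**Event-free share.** With rate λ = ln 2 / median, the share is (e^(−60λ) − e^(−120λ)) / (60λ).

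- Control, λ = 0.0231: (0.250 − 0.0625) / 1.386 = 13.5%.
- Esmolol, λ = 0.01155: (0.500 − 0.250) / 0.693 = 36%.

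**True mean difference.** 60/ln 2 − 30/ln 2 = 86.6 − 43.3 = 43 min.

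**Effect of the ceiling.** If every time beyond a ceiling L is set to L, the mean in each arm is (1/λ)(1 − e^(−λL)). The difference is then:

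- L = 60: 86.6 × 0.500 − 43.3 × 0.750 = 10.8 min
- L = 90: 86.6 × 0.646 − 43.3 × 0.875 = 18.1 min
- L = 120: 86.6 × 0.750 − 43.3 × 0.9375 = 24.3 min

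The same true effect thus gives 11 to 24 min, depending on where the ceiling falls. Under the fill rule the ceiling is the longest time observed. In simulation the filled mean difference averages about 20 min.

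**Simulated rejection rates, 32 per arm.** The power column uses the inputs above. The error column has no true effect, control median 40 min and a stay 30 min shorter in one arm. Repeat runs differ by about a percentage point.

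| Analysis | Power | Type I error |
|---|---|---|
| t-test, maximum filled in | 63% | about 6 to 7.5% |
| Mann-Whitney, maximum filled in | 60% | about 6 to 7.5% |
| t-test, event-free left out | 16 to 18% | about 20% |
| Mann-Whitney, event-free left out | about 16% | about 16% |
| Log-rank, censored at discharge | 67% | 5 to 6% |

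With event-free patients left out, the mean difference in the power scenario is about 8 min.

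**Range.** A second set used control medians of 20, 40 and 80 min and mean stays of 90 min against 90, 70 or 60 min (1,000 trials each, simulation error about 1.4 points either way).

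- Type I error was 4.9 to 8.1% with the fill, and 4.7 to 7.2% for log-rank. With event-free patients left out and shorter esmolol stays it was 8 to 19%.
- With no true effect, median 40 min and stays of 90 against 60 min, the fill gave a spurious 4 min in favour of esmolol. Leaving patients out gave a spurious 8 min against it, so the two readings err in opposite directions.
- With about 6% event-free in both arms, equal stays and no effect, every method stayed near its nominal level.

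**The case against.** The strongest reply is that the protocol has a rule and the rule works tolerably as a test. Nothing in the protocol says that event-free patients are dropped. Absent values are to be filled and the analysis is by intention to treat. With the fill, Mann-Whitney gives all untreated patients one common top rank. It loses a few points of power against log-rank and raises type I error only mildly, even with a 30 min gap in stay. With a 10 min gap the error was 5.3 to 5.4%. This stands. A reader might infer that these tests cannot be used at all, or that the plan removes the patients who did best and so nearly erases a real delay. The documents support neither: the severe figures belong to a reading that the text leaves open but does not prescribe.

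Three further replies have weight.

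- The secondary-outcome sentence is generic, and an SAP may refine it. But the protocol itself fixes the list of tests, the effect measure for all outcomes and the fill rule, and together these do not suit this endpoint.
- The gap between 20 and 43 min is partly unavoidable, since no method sees beyond discharge without extrapolation. The fault is that the horizon is set by one observed extreme instead of being chosen in advance.
- Log-rank is favoured by the simulation, which draws stays independently of need. Patients may leave early because they are comfortable, so censoring at discharge may be informative.

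**Conclusion.** The point holds in a limited form. It is certain from the text alone that the maximum-value rule runs in the favourable direction for this endpoint, and that the value for event-free patients is undefined. It follows that a mean difference with the fill has no fixed meaning: about 20 min against a true 43 min under the assumed inputs.

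The hypothesis test suffers much less. With the fill it stays close to log-rank when stays are similar. Serious loss of power (to about 16%) or inflated error (about 16 to 20% with a 30 min gap in stay) arises only if event-free patients are left out.

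All sizes rest on assumed medians, stays and hazard ratio. They shrink to nothing if nearly every patient needs an analgesic in PACU, a share that the protocol does not give. This should be corrected, but it touches one secondary endpoint and leaves the primary analysis and the 32 per group unchanged.

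**What to change.** 1. Define the time origin as PACU arrival, and state whether the event is the first analgesic or the first opioid, since the endpoint list and the hypotheses use different terms.
2. Analyse as time-to-event: Kaplan-Meier curves by arm, a log-rank test, and a hazard ratio or a difference in restricted mean time (horizon fixed in advance) with 95% CI.
3. Censor event-free patients at readiness for PACU discharge. Add a sensitivity analysis that treats discharge without analgesic as a competing event, because discharge may relate to comfort.
4. Report the proportion needing any PACU analgesic by arm.
5. Exempt this endpoint from the maximum-value rule.

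The cost is analysis wording, plus one check. Data Collection Procedures says that opioid requirements go on the PACU record but does not name the time of the first dose, so confirm that this time is captured.
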